1.2. Study Rationale

DS-1040b is an inhibitor of the activated form of TAFIa intended to be used for the treatment of thrombotic diseases including AIS. This is the first study to assess the safety, PK, and PD of a single, IV dose of DS-1040b in subjects with AIS.

1.3. Risks and Benefits for Study Subjects

No clinical studies have been conducted in human subjects to evaluate the efficacy of DS-1040b. However, the results from nonclinical studies suggest treatment with DS-1040b may enhance fibrinolysis in thromboembolic disease.

No anticipated risks of DS-1040b have been established. Overall, IV infusion of DS-1040b was safe and well tolerated in healthy young and elderly subjects. All TEAEs in the 2 completed Phase 1 clinical studies were mild or moderate in severity. None of the moderate TEAEs were considered to be drug related. No deaths, drug-related SAEs, or discontinuations were reported in the completed clinical studies.

1.4. Population, Route, Dosage, Dosage Regimen, Treatment Period

DS-1040b will be administered as a single, IV infusion. It will be administered in doses of 0.6, 1.2, 2.4, 4.8, or 9.6 mg. The single, IV infusion will consist of an initial loading dose (25% of the total dose) administered as a 0.5-hour infusion followed by a maintenance dose (75% of the total dose) administered as a 5.5-hour continuous infusion. See Section 3 for a detailed description of the overall study design.

1.5. Compliance Statement, Ethics and Regulatory Compliance

This study will be conducted in compliance with the protocol, the ethical principles that have their origin in the Declaration of Helsinki, the International Conference on Harmonisation consolidated Guideline E6 for Good Clinical Practice (GCP) (CPMP/ICH/135/95), United States (US) Food and Drug Administration GCP Regulations: Code of Federal Regulations (CFR) Title 21, parts 11, 50, 54, 56, and 312, as appropriate, and other applicable local regulations.

1.5.1. Subject Confidentiality

The Investigators and the Sponsor will preserve the confidentiality of all subjects taking part in the study, in accordance with GCP and local regulations.

The Investigator must ensure that the subject's anonymity is maintained. On the electronic Case Report Forms (eCRFs) or other documents submitted to DSPD and/or its contract research organization (CRO) designee, subjects should be identified by a unique subject identifier as designated by the Sponsor. Documents that are not for submission to DSPD and/or the CRO (eg, signed Informed Consent Forms [ICFs]) should be kept in strict confidence by the Investigator.

In compliance with applicable local guidelines and International Conference on Harmonisation GCP guidelines, it is required that the Investigator and institution permit authorized representatives of the company, of that the regulatory agency(s), and the Ethics Committee (EC) or Institutional Review Board (IRB) direct access to review the subject's original medical records for verification of study-related procedures and data. The Investigator is obligated to inform the subject that his/her study-related records will be reviewed by the above named representatives without violating the confidentiality of the subject.

1.5.2. Informed Consent Procedure

Before a subject's participation in the study, it is the Investigator's responsibility to obtain freely given consent, in writing, from the subject or legally acceptable representative after adequate explanation of the aims, methods, anticipated benefits, and potential hazards of the study and before any protocol-specific screening procedures or any study drugs are administered. A legally acceptable representative is an individual or other body authorized under applicable law to consent, on behalf of a prospective subject, to the subject's participation in the clinical study. The written ICF should be prepared in the local language(s) of the potential subject population.

In obtaining and documenting informed consent, the Investigator should comply with the applicable regulatory requirements, and should adhere to GCP and to the ethical principles that have their origin in the Declaration of Helsinki. The consent form and any revision(s) should be approved by the IRB/EC prior to being provided to potential subjects.

The subject's written informed consent should be obtained prior to his/her participation in the study, and should be documented in the subject's medical records, as required by 21 CFR Part 312.62. The ICF should be signed and personally dated by the subject or a

legally acceptable representative, and by the person who conducted the informed consent discussion (not necessarily the Investigator). The original signed ICF should be retained in accordance with institutional policy, and a copy of the signed consent form should be provided to the subject or legal representative. The date and time (if applicable) that informed consent was given should be recorded on the eCRF.

If the subject or legally acceptable representative cannot read, then according to International Conference on Harmonisation GCP Guideline, Section 4.8.9, an impartial witness should be present during the entire informed consent discussion. This witness should sign the ICF after the subject or the legally acceptable representative has orally consented to the subject's participation and, if possible, signed the ICF. By signing the ICF, the witness attests that the information in the ICF and any other written information was adequately explained to and apparently understood by the subject or the legally acceptable representative and that informed consent was freely given by the subject or the legally acceptable representative.

Suggested model text for the ICF for the study and any applicable subparts (genomic, PK, etc.) and assent forms for pediatric subjects (if applicable) are provided in the Sponsor ICF template for the Investigator to prepare the documents to be used at his or her site. Updates to applicable forms will be communicated via letter from the Clinical Study Manager.

The consent for pharmacogenomics (PGx) sampling should be documented in the subject's written informed consent. The PGx ICF should be signed and personally dated by the subject or the subject's legal representative prior to his/her participation in the study. Participation in PGx sampling is optional for all subjects. Those subjects who choose not to provide a sample for PGx sampling may still participate in the main portion of the study.

For subjects participating in this study at sites in the US, an additional consent is required for the Health Insurance Portability and Accountability Act.

1.5.3. Regulatory Compliance

The study protocol, subject information and ICF, the Investigator brochure, any subject diary card or written instructions to be given to the subject, available safety information, subject recruitment procedures (eg, advertisements), information about payments and compensation available to the subjects, and documentation evidencing the Investigator's qualifications should be submitted to the IRB/EC for ethical review and approval according to local regulations, prior to the study start. The written approval should identify all documents reviewed by name and version.

Changes in the conduct of the study or planned analysis will be documented in a protocol amendment and/or the Statistical Analysis Plan (SAP).

The Investigator must submit and, where necessary, obtain approval from the IRB/EC and/or DSPD for all subsequent protocol amendments and changes to the ICF or changes of the investigational site, facilities, or personnel. The Investigator should notify the IRB/EC of deviations from the protocol or SAEs occurring at the site and other adverse event reports received from DSPD and/or the CRO, in accordance with local procedures.

As required by local regulations, the DSPD local Regulatory Affairs group will insure all legal aspects are covered, and approval of the appropriate regulatory bodies obtained, prior to study initiation, and that implementation of changes to the initial protocol and other relevant study documents happen only after the appropriate notification of or approval by the relevant regulatory bodies.

2. STUDY OBJECTIVES AND HYPOTHESES

2.1. Study Objectives

2.1.1. Primary Objective

The primary objective of the study is to assess the safety and tolerability of DS-1040b (IV infusion over 6 hours) in subjects with AIS within 3 to 8 hours after stroke symptom onset.

2.1.2. Secondary Objectives

The secondary objectives of the study are as follows:

- To assess the plasma and urinary PK of DS-1040b in subjects with AIS.
- To assess the effect of DS-1040b on fibrinolysis biomarkers in subjects with AIS.
- To assess the effect of DS-1040b on recanalization at 24 hours in subjects with AIS.
- To assess the effect of DS-1040b on neurological outcome by using the National Institute of Health Stroke Scale (NIHSS) and functional outcome by using the modified Rankin Scale (mRS) in subjects with AIS.

2.2. Study Hypothesis

Within the dose range evaluated, DS-1040b will be safe and tolerable in subjects with AIS.

3. STUDY DESIGN

3.1. Overall Plan

3.1.1. Study Type

This is a Phase 1b/2, double-blind (Principal Investigators and study subjects blinded, Sponsor unblinded), placebo-controlled, randomized, single-ascending dose, multi-center study to assess the safety, tolerability, PK, and PD of DS-1040b in subjects with AIS.

3.1.2. Treatment Groups

This study will consist of 5, sequential, ascending-dose cohorts. A total of 64 to 80 subjects with AIS will be enrolled: 8 to 16 subjects each in Cohorts 1 and 2, and 16 subjects each in Cohorts 3, 4, and 5. In each dose cohort, subjects will be randomized to DS-1040b or placebo in a 3:1 ratio. The Principal Investigator and the subject will be blinded to the subject's assignment to either DS-1040b or placebo. Each subject will receive a single, IV infusion of DS-1040b or placebo. The single, IV infusion will consist of an initial loading dose (25% of the total dose) administered as a 0.5-hour infusion, followed by a maintenance dose (75% of the total dose) administered as a 5.5-hour continuous infusion. The planned dose level for each cohort is listed below in Table 3.1.

Table 3.1: Treatment Groups

Cohort	Number of Subjects	DS-1040b Treatment per Subject
1	6 (or 12) ^a	0.6 mg: loading dose of 0.15 mg IV infusion over 0.5 hour, followed by a maintenance dose of 0.45 mg IV infusion over 5.5 hours
	2 (or 4) ^a	Placebo
2	6 (or 12) ^a	1.2 mg: loading dose of 0.3 mg IV infusion over 0.5 hour, followed by a maintenance dose of 0.9 mg IV infusion over 5.5 hours
	2 (or 4) ^a	Placebo
3	12	2.4 mg: loading dose of 0.6 mg IV infusion over 0.5 hour, followed by a maintenance dose of 1.8 mg IV infusion over 5.5 hours
	4	Placebo
4	12	4.8 mg: loading dose of 1.2 mg IV infusion over 0.5 hour, followed by a maintenance dose of 3.6 mg IV infusion over 5.5 hours
	4	Placebo
5	12	9.6 mg: loading dose of 2.4 mg IV infusion over 0.5 hour, followed by a maintenance dose of 7.2 mg IV infusion over 5.5 hours
	4	Placebo

IV = intravenous.

a: Cohort 1 and 2 will start with an initial cohort of 8 subjects (6 active and 2 placebo). An expansion cohort of another 8 subjects (6 active and 2 placebo) may be added during the study.

Dosing in the successive cohort will occur only after completion of the blinded safety data review (up to discharge) from the previous dose cohort. Upon completion of this

blinded safety data review, a dose escalation decision will be made and the dose of the next cohort may be modified (reduced or repeated). Unblinded data will also be used by the Sponsor to perform PK and PD data analysis during the study.

Dose escalation based on symptomatic intracranial hemorrhage (sICH) criteria will be conducted in the following manner:

Cohort 1 will start with 8 subjects (6 active and 2 placebo; Cohort 1a). If no sICH is observed in the 6 active-treated subjects, Cohort 2 will start after the dose escalation safety data review. If 1 instance of sICH is observed in 1 of the 6 active-treated subjects of Cohort 1a, an expansion cohort (Cohort 1b) of 8 subjects (6 active and 2 placebo) will be enrolled and treated at the same dose level as Cohort 1a. If no sICH is observed in Cohort 1b, Cohort 2 will start after the dose escalation data review. If 1 sICH is observed in Cohort 1b, the predefined stopping criteria of sICH (2 out of 12 active-treated subjects) will be considered met and no further dose escalation will occur (refer to Section 3.1.6).

Cohort 2 will be conducted in the same manner as Cohort 1.

In Cohorts 3, 4, and 5, 16 subjects will be enrolled in each cohort. Within each cohort, if sICH is observed in 2 out of 12 active-treated subjects, sICH stopping criteria will be considered met and no further dose escalation will occur. Following an in-depth safety data review, the study may be terminated or continued with a modified (lower) dose.

Additionally, if 4 or more cases of sICH in the active-treated subjects are observed across all completed cohorts at any time during the study, the stopping criteria for sICH will be considered met and no further dose escalation will occur; however, the study may proceed at a lower dose.

Each randomized subject will receive a single, IV infusion (administered over 6 hours) of DS-1040b or placebo on Day 1. Subjects will remain hospitalized for at least 24 hours after the start of the infusion. After 24 hours, the Principal Investigator may discharge the subject at his/her discretion after completing early discharge procedures (Section 6.5). Subjects will return to the clinic on Day 30 ± 7 days for follow-up assessments. A follow-up assessment on Day 90 ± 7 days will be conducted by phone.

For additional details of the study procedures and the Schedule of Events see Section 6 and Section 17.5, respectively.

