3.1.6. Stopping Rules

The following criteria will be used to stop dose escalation during the study:

Symptomatic intracranial hemorrhage within 36 hours following the start of infusion:

- 2 cases of sICH in active-treated subjects per dose level
- 4 cases of sICH in active-treated subjects cumulatively across dose levels

Other major bleeding (non-ICH) during hospitalization and up to 5 days following the start of infusion:

- 2 cases of major bleeding defined as Thrombolysis in Myocardial Infarction (TIMI) in active-treated subjects per dose level

Other:

- In addition, DSPD, the PAREXEL Medical Monitor, and the Investigator may decide to halt dose escalation under other circumstances, such as data indicating organ toxicity, even if it is not covered by any of the prespecified stopping rules.

If any of the above criteria are met within a dose group (or across dose groups for sICH), escalation to a higher dose level will not proceed. Following an in depth review of all safety data available across the study, one of the following recommendations will be made:

- Terminate the study.
- Continue with the study but at a modified dose (eg, a dose between the current dose and the previous lower dose).
- Continue with the study but expand either the current or next cohort by an appropriate number (8 to 16) of subjects for more detailed safety evaluation.

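### The escalation review's data can end at discharge (allowed from 24 h), up to 12 h before the 36 h sICH stopping window closes; the risk is a delayed decision, not a lost case

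*Combined protocol and SAP*

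**What the plan says.** Section 3.1.2, repeated in the synopsis, defines the gate between cohorts: "Dosing in the successive cohort will occur only after completion of the blinded safety data review (up to discharge) from the previous dose cohort". The same section sets the minimum stay: "Subjects will remain hospitalized for at least 24 hours after the start of the infusion". From then on the investigator may discharge. Sections 6.2 and 6.5 schedule nothing between discharge and the Day 30 visit.

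Section 3.1.6 sets the time window for the main stopping criterion: "Symptomatic intracranial hemorrhage within 36 hours following the start of infusion". One threshold is "2 cases of sICH in active-treated subjects per dose level"; the other is four such cases across dose levels. When a criterion is met, "escalation to a higher dose level will not proceed". Section 3.1.2 applies the cumulative rule to cases "observed across all completed cohorts at any time during the study".

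Cohorts 1 and 2 have an extra step. For Cohort 1, "If no sICH is observed in the 6 active-treated subjects, Cohort 2 will start after the dose escalation safety data review". With one case among the six, a further 8 subjects (6 active, 2 placebo) are enrolled at the same dose as Cohort 1b. Cohort 2 follows the same pattern.

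Section 11.9 says the review covers bleeding, other adverse events and safety laboratory data for each completed dose level. It does not say how long a subject must have been followed for the dose level to be complete.

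**The concern.** The review is there to apply the sICH criterion, yet its stated data cut is tied to a different event (discharge) that may come before the criterion's window has closed. Read literally, the group can decide to escalate before every active-treated subject has been observed for the 36 hours that the rule counts.

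The error runs one way. A case absent from the review can only favor escalation, and each planned step doubles the dose (0.6, 1.2, 2.4, 4.8, 9.6 mg). The primary objective is safety, and the sICH rule is one of its main guards, so the review's data should cover the rule's whole window.

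**Working it through.** The plan gives no figure of its own to reproduce on this point. The check compares its times and follows one absent case through the rules.

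**1. Same clock.** The minimum stay (Section 3.1.2) and the stopping window (Section 3.1.6) are both counted from the start of infusion. Section 6 counts postdose times the same way.

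**2. Size of the gap.** For discharge at time t hours, the part of the window after discharge is 36 − t for 24 ≤ t < 36, and 0 for t ≥ 36. The maximum is 36 − 24 = 12 h, which is 12/36 = one third of the window.

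**3. Does anything else cover the gap?**
- The 24 h assessments (Section 6.2) and the discharge assessments (Section 6.5) come before it.
- The 48 h assessments (Section 6.3) apply only to subjects still in hospital.
- Adverse events are collected to Day 90 (Section 9.1), and serious ones are reported within 24 hours of awareness (Section 9.3.1). Neither is tied to the review, and after discharge awareness depends on someone telling the site.
- No section requires 36 h of follow-up, or a contact at 36 h, before the review.

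**4. Which decisions can one absent case change?**

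| Decision point | Case in the review | Case absent | When reported later |
|---|---|---|---|
| Cohort 1a or 2a, first case in 6 active | Same-dose expansion | 0 of 6: next dose opens | Alone it meets neither sICH threshold in 3.1.6 (2 per dose, 4 in total). Expansion or a halt remains available under 3.1.2, 3.1.6 and 11.10 |
| Cohort 1b or 2b, second case at that dose | Escalation stops | 1 of 12: next dose opens | Per-dose threshold met, late |
| Cohort 3 or 4, second case in 12 active | Escalation stops | 1 of 12: next dose opens | Per-dose threshold met, late |
| Fourth case in total | Escalation stops | 3 cases: next dose opens | Cumulative threshold met, late |

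Cohort 5 is the last planned dose, so four escalation decisions are exposed.

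**5. Who is exposed?** Only subjects discharged before 36 h. Among these, mainly the last treated in a cohort, because for the others there has been time for a report to arrive. As a rough scale, 64 to 80 subjects in about 15 months is 64/15 = 4.3 to 80/15 = 5.3 per month. At that average, 8 subjects take about 8/5.3 = 1.5 to 8/4.3 = 1.9 months, and 16 take about twice as long. At a typical review most of the cohort is therefore weeks past 36 h.

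**6. What cannot be calculated.** The documents give no rate of discharge before 36 h, no distribution of sICH onset, and no rate at which events after discharge go unreported. Any probability of a missed case would rest wholly on assumed inputs, so none is given.

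**The case against.** The strongest reply is that the parenthesis about discharge only describes the review, while the operative rule is Section 3.1.6, which has no discharge cut. The external ICH reviewers and the medical monitors attend the review (Section 11.9), and nothing tells them to ignore a known sICH because it followed discharge. By definition sICH involves clinical deterioration caused mainly by the hemorrhage (Section 9.9.1). After discharge it would probably mean readmission and a serious adverse event report.

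Exposure is also limited. The full schedule runs to Day 5, and subjects judged fit to leave at 24 to 36 h are plausibly at lower risk. The infusion ends at 6 h. In healthy subjects concentrations fell below 10% of the end-of-infusion value by 12 h after a 24-hour infusion (Section 1.1.1.5); a similar fall here would be complete by 6 + 12 = 18 h.

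Most of this stands, and it limits the consequence. It does not remove the mismatch. Expecting the group to look past its stated data cut is not the same as requiring 36 h of observation. The pharmacokinetic argument is incomplete too: elimination is slower in elderly subjects (Section 1.1.1.5), enrollment runs to age 80, and antiplatelet agents become allowed at 24 h (Section 5.2), just as the gap can open.

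A reader might go further and infer that a late single case in Cohort 1a or 2a has no remedy. The text does not support that. The expansion clause in Section 3.1.2 carries no time limit, and the footnote to Table 3.1 lets an expansion be added during the study. Section 11.10 allows one when more information is needed, and Section 3.1.6 lets escalation be halted outside the listed criteria. What is missing is a statement of which of these applies once the next cohort has begun.

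**Conclusion.** The mismatch is real. As written, the review can be held with up to 12 h of the 36 h sICH window unobserved for any subject discharged between 24 and 36 h. The consequence is a delayed stopping trigger, or a delayed or discretionary Cohort 1b or 2b expansion, after the next cohort has started at double the dose. The size is unknown and probably small. That judgment assumes that discharge before 36 h is uncommon in this population and that most sICH after discharge would be reported promptly; the documents state neither.

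Two further inferences are not supported:
- That the rule loses a calculable part of its power to stop. That would treat late cases as never counted, whereas under Section 3.1.6 they count when reported, and every input would be assumed.
- That the 5-day rule for other major bleeding has the same gap. Its wording mentions hospitalization and does not settle whether bleeding after discharge is meant, so nothing here rests on it.

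This is a cheap improvement to subject safety. It does not show that the escalation design fails.

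**What to change.** - In the synopsis and Section 3.1.2, replace *(up to discharge)* with *(through discharge or 36 hours after the start of infusion, whichever is later, including all AEs/SAEs reported by the time of the review)*.
- In Section 11.9, define a completed dose level in the same way.
- In Sections 6.2, 6.5 and 17.5, add a documented phone call to confirm status at 36 h for any subject discharged earlier.
- In Section 3.1.2, state that an sICH inside the 36 h window but reported after the review is applied to that cohort's decision, including the 1-of-6 expansion in Cohorts 1 and 2.

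The cost is protocol wording, one call per subject discharged before 36 h, and a wait of at most about 12 h per escalation. Over four escalations that is 4 × 12 = 48 h, or about 2 days in a study of about 15 months. Dosing at the next level would be interrupted only if a late case actually occurred. No dose, sample size or endpoint changes.
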